13.5 Pharmacokinetic Analyses

The statistical analysis of pharmacokinetic parameters will be done by the HMR Statistics and Data Management Department.

All pharmacokinetic analyses, summaries, and listings will be generated using the pharmacokinetic analysis set.

The pharmacokinetic parameters will be listed in tables of individual values and aggregated in summary tables. Descriptive statistics (sample size, mean, standard deviation, coefficient of variation [%CV], standard error of the mean, minimum, maximum, and median) will be calculated at each evaluation timepoint for plasma concentrations of YF476.

Individual, mean and median plasma concentration-time data will be presented graphically.

The relationship between PK concentrations and plasma CgA concentration or serum gastrin concentration will be examined using a graphical approach.

13.6 Safety Analyses

Summaries and listings of safety data will be generated using the safety analysis set.

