and CYP2C8 are listed in Appendix B. Guidance about assessing the risk and managing drug-drug interactions is also provided in Appendix B. All medications (prescription and over-the-counter), vitamin and mineral supplements, and/or herbs taken by the patient will be documented in the CRF at baseline, and the patient will record any new concomitant medications in the diary card, which will be checked at each visit.

Risk from study procedures: endoscopy

Patients who take part in the trial must undergo endoscopy at baseline and at the Week 12 visit. All patients in the study will have had at least one endoscopy before the trial. Most gastroscopies are done without any problem. Some people have a sore throat for a day or so afterwards. Patients may feel tired or drowsy for several hours after sedation. There is a slightly increased risk of developing a chest infection after endoscopy. Rarely, the endoscope damages the esophagus, causing bleeding or infection. Patients will be given information on how to prepare for their endoscopy according to local procedures.

Overall, the potential benefits to the trial patients of taking part in the trial greatly outweigh the risks of any harm.

5 Patient selection

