8.2 Baseline testing and pre-study evaluation

Visit 1: registration

Patients will attend the clinic and complete the informed consent form. The investigator will complete the following evaluation for each patient, and enter the data from this visit, and all subsequent visits, on the appropriate page of the CRF:

- review of most recent endoscopy (within 3 years) to confirm diagnosis of Barrett's esophagus with no dysplasia;
- review of medication history to determine that participants meet the inclusion criteria (daily PPI use for at least the most recent 12 months before study entry, and stable PPI dose for at least the most recent 3 months before study entry);
- medical history, physical examination, ECG and vital signs;
- blood and urine samples for laboratory safety tests; and
- urine pregnancy test (pre-menopausal women only).

Visit 2: baseline

Visit 2 may occur on the same day or up to 2 weeks after Visit 1. The patient will fast for 6 hours before the study visit. The investigator will complete the following evaluation for each patient, and enter the data from this visit, and all subsequent visits, on the appropriate page of the CRF. If Visits 1 and 2 are combined, only 1 blood sample (safety tests, fasting serum gastrin, plasma CgA and serum for storage) and 1 urine sample will be taken, and ECG, vital signs and pregnancy tests will be done only once.

- blood and urine samples for laboratory safety tests, urine pregnancy test (pre-menopausal women only), ECG and vital signs;
- blood samples for fasting serum gastrin, plasma CgA and serum for storage;
- endoscopy and biopsies; and
- randomization to 25 mg YF476 or placebo, and dispensing of study medication (a 42-day supply, plus overage: 1 bottle of 25 mg YF476 or placebo containing 46 capsules).

The investigator will then:

- give the patient a diary card;
- tell the patient to start taking their study medication the day after Visit 2;
- remind the patient to fast before the Week 6 visit (6 weeks after starting study medication); and
- remind the patient not to take their study medication at home on the day of the Week 6 visit, but instead to bring their container of study medication with them to the visit, and take their dose at the clinic, after the fasting blood tests.

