11.1 Adverse events (AEs)

- **Reportable adverse events**

All adverse events that occur after the informed consent is signed will be recorded on the adverse event CRF whether or not related to study medication.

- **AE data elements**

- AE reported date
- AE Verbatim Term
- SOC (System Organ Class from MedDRA)
- Common Terminology for Adverse Events v4.0 (CTCAE) AE term
- Event onset date and event ended date
- Severity grade
- Attribution to study medication (relatedness)
- Whether or not the event was reported as a Serious Adverse Event (SAE)
- Whether or not the patient dropped due to the event
- Action taken with the study medication
- Outcome of the event
- Comments

- **Severity of AEs**

Adverse events will be identified using the NCI Common Terminology Criteria for Adverse Events (CTCAE) version 4.0. The CTCAE provides descriptive terminology and a grading scale for each adverse event listed. A copy of the CTCAE can be found

at http://ctep.cancer.gov/protocolDevelopment/electronic_applications/ctc.htm#ctc_40

AEs will be assessed according to the CTCAE grade associated with the AE term. AEs that do not have a corresponding CTCAE term will be assessed according to the general guidelines for grading used in the CTCAE v4.0, as stated below.

- **CTCAE v4.0 general severity guidelines**

(from http://evs.nci.nih.gov/ftp1/CTCAE/CTCAE_4.02_2009-09-15_QuickReference_8.5x11.pdf)

Grade	Severity	Description
1	Mild	Mild; asymptomatic or mild symptoms; clinical or diagnostic observations only; intervention not indicated.
2	Moderate	Moderate; minimal, local or noninvasive intervention indicated; limiting age-appropriate instrumental ADL*.
3	Severe	Severe or medically significant but not immediately life-threatening; hospitalization or prolongation of hospitalization indicated; disabling; limiting self-care ADL**.
4	Life-threatening	Life-threatening consequences; urgent intervention indicated.
5	Fatal	Death related to AE.

- **Activities of Daily Living (ADL)**

*Instrumental ADL refer to preparing meals, shopping for groceries or clothes, using the telephone, managing money, etc.

**Self care ADL refer to bathing, dressing and undressing, feeding self, using the toilet, taking medications, and not bedridden.

- **Assessment of relationship of AE to treatment**

The possibility that the adverse event is related to study medication will be classified as one of the following: not related, unlikely, possible, probable, definite.

- **Follow-up of AEs**

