13.1 Analysis Sets

The safety analysis set will include all patients who are randomized and receive at least one dose of study medication. In this population, treatment will be assigned based upon the treatment patients actually receive regardless of the treatment to which they were randomized.

The pharmacokinetic analysis set will include all patients who receive at least one dose of study medication, and yield at least one plasma concentration for YF476.

The Intent-to-Treat (ITT) analysis set will include all randomized patients who receive at least one dose of study medication and have at least one post-baseline assessment. In this population, treatment will be assigned based upon the treatment to which patients were randomized regardless of which treatment they actually received.

A per-protocol analysis will also be completed.

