## 9 Analysis Populations

The following populations will be identified:

Screened Population: All patients screened for the study.

Safety Population: All patients who are randomised and received at least one dose of the study drug. In this population, treatment will be assigned based upon the treatment patients actually receive regardless of the treatment to which they were randomized.

Intent-to-Treat (ITT) Population: All randomised patients who receive at least one dose of study medication and had at least one post-baseline assessment. In this population, treatment will be assigned based upon the treatment to which subjects were randomised regardless of which treatment they actually received.

Per Protocol (PP) Population: All randomized patients who receive at least one dose of study medication and had at least one post-baseline assessment and did not have any major protocol deviations.

In all populations (apart from ITT) treatment will be assigned based upon the treatment patients actually receive regardless of the treatment to which they were randomised.

The primary endpoint will be analysed using the ITT population.

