## **14 Safety Analyses**

Summaries and listings of safety data will use the safety population.

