## **19 ATTACHMENTS**

### **19.1 Table of Contents for Data Display Specifications**

For overall page layout refer to Appendix B.

The numbering in the tables below will take precedence over the numbering in the shells.

The following tables and figures will be produced (templates provided in Section 19.2.1 and 19.2.2):

Table	Description	Population	Source Listing	Template (Shells below)
10.1	Summary of patient disposition	Safety	16.2.1.2 16.2.3.1	T_SD1
10.2.1	Summary of concomitant medications	Safety	16.2.4.2	T_CM1
10.2.2	Summary of medical history: barrett's esophagus	Safety	16.2.4.3	T_MH1
10.2.3	Summary of treatment compliance	Safety	16.2.5.1	T_COMP1
14.1	DEMOGRAPHIC DATA			
14.1	Summary of demographic characteristics	Safety	16.2.4	T_DM1
14.2	PHARMACOKINETIC and EFFICACY			
14.2.1	Summary of netazepide plasma peak and trough concentration data	Safety	16.2.6.1	T_PK1
14.2.2.1	Summary of serum gastrin and plasma CgA data (ITT)	ITT	16.2.6.2	T_EG2
14.2.2.2*	Summary of serum gastrin and plasma CgA data (PP)	PP	16.2.6.2	T_EG2
14.3	SAFETY DATA			
14.3.1.1	Summary of treatment-emergent adverse events	Safety	16.2.7.1	T_AE1
14.3.1.2	Summary of drug-related treatment-emergent adverse events	Safety	16.2.7.1	T_AE1
14.3.2.1	Listing of fatal adverse events	Safety	16.2.7.1	L_AE1_PG
14.3.2.2	Listing of non-fatal serious adverse events	Safety	16.2.7.1	L_AE1_PG
14.3.2.3	Listing of other significant adverse events	Safety	16.2.7.1	L_AE1_PG
14.3.3	Narratives of deaths, other serious and significant adverse events	Safety	-	-
14.3.4	Summary of laboratory values of potential clinical importance	Safety	16.2.8.1, 16.2.8.3	T_LB1
14.3.5.1	Summary of chemistry laboratory values	Safety	16.4	T_LB2
14.3.5.2	Summary of haematology laboratory values	Safety	16.4	T_LB2
14.3.5.3	Summary of urinalysis results	Safety	16.4	T_UR1
14.3.6.1	Summary of vital signs	Safety	16.4	T_VS1
14.3.7.1	Summary of ECG values	Safety	16.4	T_EG2
14.3.7.2	Summary of ECG values and changes in ECG values of potential clinical importance	Safety	16.4	T_EG3

Figure	Description	Population	Source Listing	Template (Shells below)
14.3	SAFETY AND EFFICACY DATA			

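### An SAE at the baseline endoscopy that prevents dosing would be missing from the report's fatal-event listing, SAE listing and narratives, because those outputs are limited to dosed patients

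*Protocol*

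**What the plan says.** Both documents tie safety output to dosing, and both name listings as well as summaries. Protocol 13.6: "Summaries and listings of safety data will be generated using the safety analysis set". SAP 14: "Summaries and listings of safety data will use the safety population". The set is defined in Protocol 13.1 ("The safety analysis set will include all patients who are randomized and receive at least one dose of study medication") and in equivalent terms in SAP 9 ("All patients who are randomised and received at least one dose of the study drug").

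Collection of adverse events starts earlier. Protocol 11.1: "All adverse events that occur after the informed consent is signed will be recorded on the adverse event CRF", whether or not they are related to study medication. The baseline endoscopy is at Visit 2. Protocol 10.1 adds six research biopsies to the routine ones, and Protocol 8.2 has the investigator "tell the patient to start taking their study medication the day after Visit 2". Protocol 4.3 foresees procedural harm: "Rarely, the endoscope damages the esophagus, causing bleeding or infection".

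The table index in SAP 19.1 gives the population Safety to 14.3.2.1 (fatal adverse events), to 14.3.2.2 ("Listing of non-fatal serious adverse events") and to 14.3.3 (narratives). The listings index in the same section has no population column, so 16.2.7.1 (all adverse events), 16.2.7.2 (SAEs) and 16.2.7.3 (adverse events leading to withdrawal) carry no label. Protocol 13.6.1 and SAP 14.2 each say that every adverse event is to be listed.

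**The concern.** There is an interval, from consent to the first capsule, in which events are collected but the patient is not yet in the safety set. The sedated endoscopy and the extra biopsies fall in that interval. A patient who has a serious complication there and never starts capsules stays outside the set for good, so the exclusion is selective: the harm itself removes the patient.

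The treatment-emergent tables cannot show such an event, since by definition they count only events that arise or worsen during treatment. The SAE and death listings and the narratives are therefore where a reader of the report would look for it. The disposition summary would give little warning. SAP 13.1 bases it on the safety population, and the T_SD1 shell has no row for patients randomised but not dosed. At stake is whether the SAE section of the report is complete in a small trial that names safety among its aims (Protocol 2.2).

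**Working it through.** The plan gives no figure on this point, so the check is mainly a reading of the sections against each other.

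1. **Order of events.** Consent and the start of adverse event collection come at Visit 1 (Protocol 8.2, 11.1). The endoscopy and biopsies come at Visit 2, on the same day or up to 2 weeks later. The first dose is on the day after Visit 2.

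2. **Membership of the safety set.** Protocol 7.6 allocates the patient number immediately before the endoscopy, while Protocol 8.2 lists randomisation after it. The difference does not matter here: without a dose the patient is outside the set either way. A patient who has a pre-dose SAE but later starts capsules is in the set and is listed.

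3. **Each output, for an SAE in a never-dosed patient.**

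| Output | Population stated | Result |
|---|---|---|
| 14.3.2.1 fatal events | Safety | left out |
| 14.3.2.2 non-fatal SAEs | Safety | left out |
| 14.3.3 narratives | Safety | left out |
| 16.2.7.1 and 16.2.7.2 listings | none | unclear: the opening sentences of Protocol 13.6 and SAP 14 exclude it; Protocol 13.6.1 and SAP 14.2 include it |
| 14.3.1.1 and 14.3.1.2 treatment-emergent tables | Safety | not applicable: a pre-dose event is not treatment-emergent |
| 16.2.1.2 reasons for withdrawal | no safety-set limit in SAP 13.1 | should appear, with the reason |
| Complete data listings (end of the SAP 19.1 index) | none | should appear |

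4. **Frequency.** The documents say only that such damage is rare. Let p be the assumed probability, per baseline endoscopy, of an SAE that prevents dosing. The chance of at least one among n patients is 1 − (1 − p)^n. The values of n are 20, the target number of completers, and 48, the number of patient numbers in Protocol 7.6 (24 at each of 2 sites), as a ceiling.

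| Assumed p | n = 20 | n = 48 |
|---|---|---|
| 0.1% | 2.0% | 4.7% |
| 0.5% | 9.5% | 21.4% |
| 1% | 18.2% | 38.3% |

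For example, 1 − 0.99^20 = 0.182. The expected number of events at n = 20 is 20 × 0.001 = 0.02 to 20 × 0.01 = 0.20. If p is instead read as the rate of all serious complications, these figures are upper bounds, because some of those patients would still be dosed.

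**The case against.** A reader might infer that such an SAE is certain to vanish from every SAE listing, so that the report could say there were none. The documents do not support that. Listings 16.2.7.1 to 16.2.7.3 carry no population label. Protocol 13.6.1 attaches the safety set explicitly only to the tabulation of treatment-emergent events, and it promises listings of deaths and SAEs without a limit of its own. SAP 14.2 says without qualification that all adverse events are listed. SAP 13.1 lists every withdrawn patient with the reason, SAP 12.1 includes all premature withdrawals in the analyses, and SAP 19.1 ends by promising complete data listings. This stands: outside the three labelled outputs, the text is ambiguous or inclusive.

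A reader might also infer a failure of oversight. That is not so. Protocol 11.2.2 has the sponsor and the DSMB contacted within 24 hours of any SAE, dosed or not, and under Protocol 12.1 the DSMB reviews all SAE forms and all adverse events.

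Two further points limit the weight of the matter. Protocol 15 treats the baseline endoscopy and biopsies as standard of care, and Protocol 10.1 says the same of the inspection and four-quadrant biopsies, so only the six extra biopsies are specific to the research. And the stated aim concerns the safety of YF476, about which an event in a patient who never took a capsule says nothing.

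None of this removes the Safety label from 14.3.2.1, 14.3.2.2 and 14.3.3, or settles which of the conflicting sentences governs the 16.2.7 listings.

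**Conclusion.** The point holds in a limited form. By the stated rules, an SAE that prevents dosing is left out of the fatal-event listing, the non-fatal SAE listing and the narratives. Its place in 16.2.7.1 and 16.2.7.2 is undetermined until the general and specific sentences are reconciled.

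The consequence is an incomplete SAE section in an uncommon case: about a 2% to 18% chance of at least one such event among 20 patients, resting wholly on an assumed rate of 0.1% to 1%. No event is lost to the sponsor or the DSMB. No treatment-emergent table or comparison between arms changes, and no conclusion about YF476 is affected. The priority is minor.

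**What to change.** - Keep the treatment-emergent tables and all other safety summaries on the safety population.
- Amend the opening sentences of Protocol 13.6 and SAP 14 so that listings of adverse events, SAEs and deaths, and the narratives, cover all patients who signed consent. The Screened population in SAP 9 can serve, if its definition says that it starts at consent.
- In SAP 19.1, change the population of 14.3.2.1, 14.3.2.2 and 14.3.3 accordingly, and state the same population for 16.2.7.1 to 16.2.7.3.
- Add a flag in these listings for events before the first dose and for patients never dosed.

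The cost is one sentence in each document, a few population labels and one flag. No new data are needed, because the events are already recorded from consent. The drawback is that a few pre-dose events unrelated to study drug will appear in the listings; the flag lets a reader set them apart.

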13.6.1 Adverse Event Analyses

Adverse events (AEs) will be coded using the version of the Medical Dictionary for Regulatory Activities (MedDRA) that is current when the database is locked. All AEs including serious AEs will be mapped to system organ class and preferred term, and will be listed in the data listing.

A treatment-emergent adverse event (TEAE) is defined as an AE that emerges during treatment, having been absent pre-treatment, or that worsens relative to the pre-treatment state.

The number and percentage of patients reporting TEAEs will be tabulated for the safety analysis set by MedDRA preferred term and system organ class, and further by relationship to study drug administered and by severity.

Listings of deaths, SAEs, and AEs that lead to discontinuation of a patient will be presented.

13.6.2 Analyses of Clinical Laboratory Tests

Standard haematology, biochemistry and urinalysis at each planned assessment, and change from baseline at each planned post-baseline assessment, will be summarized.

13.6.3 Electrocardiogram Analyses

The ECG variables (PR, RR, QRS, QT, QTcB, and QTcF) and heart rate (HR) at each planned assessment will be summarised. The QT intervals will be corrected for heart rate by the Bazett's and Fridericia's formula ($QTcB = QT/[RR]^{1/2}$ and $QTcF = QT/[RR]^{1/3}$). The incidence of outliers in absolute QT, QTcF and QTcB intervals (>450, >480, and >500 msec), and the change from time-matched baseline in QT, QTcF and QTcB intervals (>30 and >60 msec) will be summarised.

13.7 Determination of sample size

Based on our preliminary data, we estimate a mean baseline Ki67 index of 45–50%, with a common SD of 14–18%. Assuming a two-sided type I error rate of 0.05, a sample size of 20 (10 per arm) has 98% power to detect a 30% absolute difference in $\Delta Ki67$ between the two arms if the common SD is 16%, and 97% power for a 25% difference with a 14% common SD (see Table 1).

Table 1. Power calculations based on 20 patients (10 per arm)			
	$\Delta\text{Ki67}_{\text{YF}} - \Delta\text{Ki67}_{\text{pl}}$		
SD	0.25	0.30	0.35
0.14	97%	99%	>99%
0.16	91%	98%	>99%
0.18	84%	94%	98%

14 Ethical and regulatory considerations

This trial will be conducted in compliance with the protocol, Good Clinical Practice (GCP), and the applicable regulatory requirements.

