3.3 Rationale

As described above, clinical guidelines for the management of BE include gastric acid suppression with chronic PPI therapy. Acid reflux appears to have an important causal role in the development of BE, and a history of reflux symptoms is associated with EAC.¹² However, data are inconclusive with regard to acid suppression and EAC risk. In a retrospective study of veterans with BE, PPI compared with histamine- H_2 antagonists or no acid suppression was associated with a lower risk of progression to dysplasia.¹³ In contrast, other studies suggest that PPIs may be associated with an *increased* risk for developing EAC,¹⁴ and Feagins *et al* reported anti-proliferative effects of acid exposure in non-dysplastic BE cells.¹⁵

By inhibiting acid secretion, PPIs at therapeutic doses can cause secondary hypergastrinemia. Gastrin exerts trophic effects in BE via CCK2R activation.⁵ There is increased expression of CCK2R in BE compared to squamous epithelium, and gastrin can stimulate proliferation, anti-apoptosis, COX-2 expression, and loss of cell-cell adhesion in BE cells.^{5, 16} The chief investigator's group recently reported that BE patients with high serum gastrin levels had significantly increased odds of a history of high grade dysplasia (HGD) or EAC.⁶ In that cross-sectional study, they enrolled 95

patients with BE (with and without dysplasia or EAC) and GERD controls on chronic PPI therapy. Subjects in the highest serum gastrin quartile had significantly increased odds of a history of advanced neoplasia (adjusted OR 5.46, 95% CI 1.20–24.8). The group also analyzed 19 samples from non-dysplastic Barrett's epithelium, and found marked elevations in Ki67 expression, with a mean Ki67 index of 48.3% (SD 16.0%). They also found a moderate correlation between serum gastrin and tissue Ki67 index ($r=0.64$, $p=0.05$) in a subset of ten patients¹⁷.

Those studies support the notion that gastrin may promote carcinogenesis in BE, and that these potentially pro-neoplastic effects occur via activation of the CCK2 receptor. We therefore propose the following clinical trial to analyze the effects of a CCK2 receptor antagonist in patients with BE. The primary hypothesis is that administration of YF476, a CCK2 receptor antagonist, in patients with BE will result in a significant decrease in cellular proliferation in the Barrett's mucosa.

4 Summary of study plan

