7.6 Registration and randomization

- A member of the HMR Statistics and Data Management Department will generate a randomization list for each site. Patient numbers will be allocated to eligible patients immediately before the EGD and biopsy at Visit 2 (Baseline). Patients enrolled at CUMC will be allocated patient numbers 01–24. Patients enrolled at NIHR CIW will be allocated patient numbers 1001–1024. The lists are independent of each other. At both sites, patients on PPI once daily will be given the next available number from the top of the list, and patients on PPI twice daily will be given the next available number from the bottom of the list.
- At each site, the site coordinators will maintain a site-specific list of participants, including patient codes, start date, and duration of treatment. Every time a patient is recruited at one of the sites, the coordinator for that site will inform the chief investigator (if applicable) and the coordinator for the other site. It is the chief investigator's responsibility to ensure that the total number of study patients does not exceed the target.

The randomization list will specify whether the patient receives a dose of YF476 or placebo. Fixed allocation randomization will be performed, with equal allocation (1:1) between the 25 mg YF476 and placebo groups. Blocked randomization will be used. Randomization will be stratified by PPI dose and by site. The site pharmacy will dispense YF476 or placebo according to the randomization list. The study investigators and the study patients will remain blinded.

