13.4 Efficacy Analyses

All efficacy analyses, summaries and listings will be generated using the efficacy analysis set.

Primary efficacy variables are:

- Change in Ki67 expression (ΔKi67)

Secondary efficacy variables are:

- Changes in gene expression in BE tissue (measured by RNA-Seq).
- Change in CCK2R mRNA levels (measured by qRT-PCR)
- Change in DCAMKL1 expression (measured by IHC)
- Change in DCAMKL1 mRNA levels (measured by qRT-PCR)
- Change in COX-2 mRNA levels (measured by qRT-PCR)
- Change in p53 expression (measured by IHC)
- Change in serum gastrin and plasma CgA between baseline and Visit 5

For all efficacy variables listed above, individual values will be presented by patient and summarised by visit.

The primary endpoint (Change from baseline (Visit 2) in Ki67 expression (Δ Ki67)) will be summarised using descriptive statistics. The primary analysis for the primary endpoint will use two sample t-tests comparing between treatment groups. Nominal p-value and 95% confidence intervals for treatment difference will be reported.

To evaluate the robustness of the primary analysis, the following sensitivity analysis will also be performed:

Baseline Adjusted Analysis: this sensitivity analysis will use an analysis of covariance model with the primary endpoint as the dependent variable, treatment group as a factor and baseline (Visit 2) as a covariate. Adjusted least square means and corresponding 95% confidence interval will be reported.

Serum gastrin and chromogranin A (CgA) will be measured at baseline (Visit 2) and at Weeks 6 and 12. Analyses will be performed to determine whether there is a correlation between baseline gastrin and subsequent Δ Ki67. YF476 assays will be performed at Weeks 6 and 12.

Analysis of the secondary endpoints will be similar to the primary analysis. No sensitivity analysis is planned for these endpoints.

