## **8 Sample Size Considerations**

### **8.1 Sample Size Assumptions**

Based on preliminary data, a mean baseline Ki67 index of 45–50%, with a common SD of 14–18% was estimated. Assuming a two-sided type I error rate of 0.05, a sample size of 20 (10 per arm) has 98% power to detect a 30% absolute difference in  $\Delta$ Ki67 between the two arms if the common SD is 16%, and 97% power for a 25% difference with a 14% common SD (see Table 1).

Table 1. Power calculations based on 20 patients (10 per arm)			
	<math>\Delta\text{Ki67}_{\text{YF}} - \Delta\text{Ki67}_{\text{pl}}</math>		
SD	0.25	0.30	0.35
0.14	97%	99%	>99%
0.16	91%	98%	>99%
0.18	84%	94%	98%

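### Power for ΔKi67 rests on an SD stated for the baseline index, with no SD of change or correlation given, and the baseline-adjusted analysis is only a sensitivity analysis

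*Protocol*

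**What the plan says.** Protocol 13.7 says "we estimate a mean baseline Ki67 index of 45–50%, with a common SD of 14–18" percent and attributes this to preliminary data. SAP 8.1 repeats it: "a mean baseline Ki67 index of 45–50%, with a common SD of 14–18% was estimated". The next sentence of Protocol 13.7 applies the SD to the difference in ΔKi67 "between the two arms if the common SD is 16" percent. Table 1 then gives power of 84% to >99% for 10 per arm. The only preliminary Ki67 spread reported is in Protocol 3.3: 19 non-dysplastic samples with mean 48.3% and SD 16.0%.

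On the analysis, Protocol 13.4 states: "The primary analysis for the primary endpoint will use two sample t-tests comparing between treatment groups". The sensitivity analysis is an "analysis of covariance model with the primary endpoint as the dependent variable, treatment group as a factor and baseline (Visit 2) as a covariate". Protocol 7.6 adds "Randomization will be stratified by PPI dose and by site". In practice the PPI stratum is frequency of dosing: "patients on PPI once daily will be given the next available number from the top of the list", and twice-daily patients are numbered from the bottom. Neither model in 13.4 contains these strata.

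SAP 3 leaves the efficacy data other than gastrin and CgA to separate reporting, and SAP 4.3 plans no formal testing. Protocol 13.4 is therefore the only Ki67 model in the two documents.

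**The concern.** The SD of a change score is not the SD of a single measurement. It depends on the SD at both visits and on the correlation between them, and it can be larger or smaller than the baseline SD. The 14–18% is worded as a property of the baseline index and brackets a cross-sectional SD of 16.0%, yet Table 1 uses it for a change score. A reader cannot tell whether 20 completers give the primary test the power claimed.

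The choice of primary model adds to this. The change-score t-test is most affected by a low correlation, which is where adjusting for baseline helps most. With 20 patients, analysing change without baseline can give a wider interval than the same data need, and so a greater chance of missing a real effect.

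**Working it through.** **Inputs from the documents.** 10 per arm; two-sided 0.05; differences D of 25, 30 and 35 points; SDs of 14, 16 and 18 (Protocol 13.7, SAP 8.1). Two-sample t-test on ΔKi67, 18 df (Protocol 13.4).

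**Inputs not given.** The baseline-to-Week 12 correlation r, the Week 12 SD and the SD of change. The only Ki67 correlation reported (0.64, ten patients, Protocol 3.3) is with serum gastrin and cannot serve. I assume r from 0 to 0.7 and equal SDs at the two visits unless stated.

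**1. Reproduce Table 1.** Noncentral t with noncentrality D / (SD_Δ × √(2/10)), entering the tabled SD directly as SD_Δ. For D = 25 and SD 16 this is 25 / (16 × 0.447) = 3.49, giving 91.0%.

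| SD | 25 | 30 | 35 |
|---|---|---|---|
| 14 | 96.5% | 99.5% | 100.0% |
| 16 | 91.0% | 97.7% | 99.6% |
| 18 | 83.6% | 94.1% | 98.4% |

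All nine cells match the printed table within one point. Table 1 therefore treats 14–18% as the SD of the change.

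**2. Read 14–18% as a single-visit SD.** Then SD_Δ = SD × √(2(1 − r)). At SD 16 this is 22.6, 18.9, 16.0 and 12.4 for r = 0, 0.3, 0.5 and 0.7. It equals the tabled SD only at r = 0.5.

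**3. Compare with ANCOVA.** With equal visit SDs, the residual variance of ANCOVA relative to the change score is SD²(1 − r²) / (2·SD²(1 − r)) = (1 + r)/2, before the loss of degrees of freedom. The ANCOVA below has treatment, baseline, site and PPI frequency. It was simulated with 8,000 trials per case, 10 per arm, and strata explaining no variance. Assumed, because the documents do not give them: blocks of 4, half the patients per site, 40% on twice-daily PPI.

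Power (%) at 25 / 30 points:

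| SD | Model | r = 0 | r = 0.3 | r = 0.5 | r = 0.7 |
|---|---|---|---|---|---|
| 14 | t-test | 76 / 89 | 89 / 97 | 97 / >99 | >99 / >99 |
| 14 | ANCOVA | 94 / 99 | 96 / 99 | 98 / >99 | >99 / >99 |
| 16 | t-test | 65 / 80 | 80 / 92 | 91 / 98 | 99 / >99 |
| 16 | ANCOVA | 87 / 96 | 90 / 98 | 95 / 99 | 99 / >99 |
| 18 | t-test | 55 / 70 | 70 / 85 | 84 / 94 | 97 / >99 |
| 18 | ANCOVA | 79 / 91 | 83 / 94 | 89 / 97 | 97 / >99 |

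The Monte Carlo standard error is at most 0.5 points. Mean 95% CI width at SD 16, t-test to ANCOVA: 41.9 to 31.4, 35.1 to 29.8, 29.7 to 27.1 and 22.9 to 22.4 points. Simulated type I error is 4.7–5.1% for the t-test, the baseline-only ANCOVA and the four-term ANCOVA.

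**4. Read 16% as the SD of change.** The visit SD is then 16/√(2(1 − r)). At 25 points the t-test has about 91% power whatever r is. The four-term ANCOVA has 99, 97, 95, 92 and 90% at r = 0, 0.3, 0.5, 0.7 and 0.9.

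**5. Unequal SDs.** If the Week 12 SD differs from baseline in both arms, Table 1 holds when r ≥ SD_week12 / (2 × SD_baseline). If only the active arm's Week 12 SD falls, by an assumed ratio w, the condition is r ≥ (1 + w²)/(2(1 + w)). At w = 0.75 this is 1.5625/3.5 = 0.45. With SD 16 and 25 points, t-test against four-term ANCOVA is then 69 v 94% (r = 0), 84 v 96% (r = 0.3) and 93 v 98% (r = 0.5).

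**The case against.** The 14–18% may already be an SD of change. The protocol applies it directly to the ΔKi67 comparison, and the 19 samples in 3.3 need not be all of the preliminary data. If so, Table 1 is correct for the t-test. This cannot be ruled out, but no source for an SD of change is given, so the power is unsupported on either reading.

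The t-test on change is valid in a 1:1 randomised trial, the study is described as a pilot, and the baseline-adjusted result will be reported anyway. All true. The point about the model concerns precision, not bias, and the gain has limits. It is negligible by r = 0.7 and becomes a loss of about 1–2 points of power near r = 0.9 if 14–18% is the SD of change. At the headline 30 points and SD 16, the t-test keeps 80% power even at r = 0. The exposure is greatest at 25 points, SD 18 and low r.

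The strata terms are not in the planned ANCOVA, and they cost a little if they explain nothing. That also stands; the cost is given with the fix. Finally, a separate Ki67 analysis document may exist that settles some of this. It is not among the two supplied.

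**Conclusion.** The concern holds. Table 1 is arithmetically right for an SD of change of 14–18 points, but the documents give no basis for that input. If the figure is a single-visit SD with equal SDs at both visits, the printed power needs r of at least 0.5. Across r = 0 to 0.7, the 98% headline (30 points, SD 16) becomes 80% to >99%, and the 97% headline (25 points, SD 14) becomes 76% to >99%. The true power could be below or above what is stated.

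Under either reading of the SD, the t-test gives a wider interval than the baseline-adjusted model for r up to about 0.7. The difference is large at low r (41.9 against 31.4 points at r = 0, SD 16) and small at r = 0.7. These comparisons rest on normal data and on the assumed stratum proportions and block size. This should be fixed; it does not invalidate the trial.

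**What to change.** Before the blind is broken:

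1. In Protocol 13.4, and in whichever document governs the separately reported Ki67 analysis, make the planned baseline-adjusted ANCOVA of ΔKi67 primary, with site and PPI frequency (once or twice daily) as further terms. Keep the two-sample t-test as the sensitivity analysis.
2. In Protocol 13.7 and SAP 8.1, say whether 14–18% is a single-visit SD or an SD of change, and give its source. If single-visit, state the equal-SD assumption and replace Table 1 with power for the chosen primary model over r = 0 to 0.7; the ANCOVA rows above would serve. If it is an SD of change, say so; Table 1 then stands for the t-test only. The printed Table 1 should not be attached to any ANCOVA.

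**Cost.** No extra patients or samples. A protocol amendment goes to the IRBs (14.1.3) and, for Cambridge, presumably to the bodies named in 14.2. Protocol 13.2 also allows departures from the planned analysis to be described in the SAP. Residual degrees of freedom fall from 18 to 15.

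If site and PPI explain nothing, adding them to the baseline ANCOVA widens the interval by 0.5–0.8 points and costs up to about 2 points of power (25 points, SD 16: 89 to 87% at r = 0, 92 to 90% at r = 0.3). That is recovered if they explain about 5% of residual variance, a figure the documents do not give.
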